- Week 1: 6 mg AZD4573 once weekly and 100 mg acalabrutinib twice daily
- Week 2: 9 mg AZD4573 once weekly and 100 mg acalabrutinib twice daily
- Week 3: 12 mg AZD4573 once weekly and 100 mg acalabrutinib twice daily
- Week 4: 12 mg AZD4573 once weekly and 100 mg acalabrutinib twice daily
- Week 5: 12 mg AZD4573 once weekly and 100 mg acalabrutinib twice daily

Dose Level -1: Once-weekly IV administration of AZD4573 with oral administration of acalabrutinib 100 mg twice daily continuously.

- Week 1: 1.5 mg AZD4573 once weekly and 100 mg acalabrutinib twice daily
- Week 2: 3 mg AZD4573 once weekly and 100 mg acalabrutinib twice daily
- Week 3: 6 mg AZD4573 once weekly and 100 mg acalabrutinib twice daily
- Week 4: 6 mg AZD4573 once weekly and 100 mg acalabrutinib twice daily
- Week 5: 6 mg AZD4573 once weekly and 100 mg acalabrutinib twice daily

Upon completion of the 5-week DLT-assessment period, participants will remain on their target dose level of AZD4573 administered intravenously once weekly in combination with daily orally administered acalabrutinib 100 mg twice daily in 3-week treatment cycles until disease progression, an unacceptable drug-related toxicity occurs as defined in the protocol, or the participant withdraws or is withdrawn from the study for other reasons. No further intra-patient dose escalation (other than the ramp up to the assigned target dose level) will be allowed.

After completion of the 5-week DLT-assessment period, dose reduction of AZD4573 with each cycle or within a cycle may be applied, on an individual participant basis, based upon the grade of toxicity experienced by the participant. Dose modification provisions are provided in Section [15.12](#). All participants who discontinue study treatment (ie, both drugs) will have a SFU visit 30 (\pm 7) days after the last dose of study drug(s).

All participants will be followed for survival until death, loss to follow-up, AstraZeneca closes the study, or withdrawal of consent, whichever occurs first.

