- Grade ≥ 3 clinical TLS ([Appendix F](#)) that occurs despite protocol-recommended management will be considered a DLT.
- Laboratory TLS ([Appendix F](#)) will be considered a DLT if the metabolic abnormalities do not resolve within 5 days despite protocol-recommended management.

Note: All DLT events of TLS should be graded according to the Howard modification of the Cairo-Bishop criteria as part of TLS monitoring (Section [17.1.5](#) and [Appendix F](#)), while CTCAE grade should be applied on AE/SAE reports.

The definition of DLT excludes:

- 1 Grade 3 fatigue for ≤ 7 days after onset.
- 2 Isolated laboratory changes of any grade without clinical sequelae or clinical significance, with the exception of transaminase and bilirubin abnormalities described above.
- 3 Isolated changes in GGT (ie, with no corresponding elevation in AST, ALT, ALP, Total bilirubin or INR, and no symptoms suggestive of hepatic injury) will not be classified as a DLT.

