In general, if a participant experiences a Grade 1 or Grade 2 haematological or non-haematological toxicity, no dose modification is required. If a participant experiences a Grade 3 or Grade 4 toxicity, not attributable to the disease or disease-related processes under investigation, dosing might be interrupted and/or the dose reduced (see [Table 12](#) for acalabrutinib reduction options and [Table 13](#) for recommended dose modifications for AZD4573 and acalabrutinib) and supportive therapy administered as required. If the toxicity resolves or reverts to CTCAE Grade ≤ 2 within 21 days and the participant was showing clinical benefit, treatment with study treatment(s) may be restarted.

If the toxicity does not resolve to CTCAE Grade ≤ 2 within 21 days, then the participant should be withdrawn from the study and observed until resolution of the toxicity. Maximal drug interruption allowed for related toxicity for both AZD4573 and acalabrutinib is ≤ 21 consecutive days.

Table 13 Recommended Dose Modifications for AZD4573 and Acalabrutinib

Event ^a	Occurrence	Action with AZD4573	Action with Acalabrutinib
Tumour Lysis Syndrome (TLS) – Howard Modification of Cairo-Bishop Criteria			
Changes in uric acid, potassium, phosphorus, creatinine or calcium, or symptoms suggestive of clinically significant TLS, in the Investigator's judgement	Any	For any abnormal changes present before dosing, initiate supportive therapy and hold drug for up to 7 days. If not resolved, reduce by 1 dose level.	Withhold acalabrutinib until resolved, resume dosing at the same dose level upon resolution.
		For events of Grade 1 or 2 TLS, resume at same dose level upon resolution.	For events of Grade 1 or 2 TLS, resume at same dose level upon resolution.
		For 1st occurrence of Grade 3 TLS resume at the same dose upon resolution to Grade 1.	For 1st occurrence of Grade 3 TLS resume at the same dose upon resolution.

Table 13 Recommended Dose Modifications for AZD4573 and Acalabrutinib

Event ^a	Occurrence	Action with AZD4573	Action with Acalabrutinib

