15.12.1 Retreatment Criteria

Retreatment is defined as the first dose of study drug after a significant period of intentional pause in study drug treatment (other than missed doses, eg, study treatment put on hold until resolution of COVID-19).

Retreatment criteria (criteria to be met before participant restarts study drug infusions [and capsules, as applicable]):

All participants:

- 1 Participant has recovered from all treatment-related non-haematological toxicity to CTCAE Grade ≤ 2 .
- 2 Recovery of neutrophils $\geq 1000/\mu\text{L}$ and platelets $\geq 50,000/\mu\text{L}$.
- 3 Participant has recovered from all hepatic toxicity events within the timeframes described in Table 14 above. If biochemical changes in transaminase(s) and total bilirubin are consistent with the definition of HL, the participant may continue to receive study drug

only if all abnormalities have resolved within the timeframes specified in [Table 14](#) above, there are no symptoms of liver injury and INR has not increased above $1.5 \times$ ULN (or $1.5 \times$ baseline). In these circumstances the participant must be made aware of the unknown potential for liver damage with continued exposure to AZD4573 prior to retreatment. Documentation of continued consent is required.

- 4 Recovery of uric acid to $<$ ULN.
- 5 Recovery of changes in uric acid, potassium, phosphorus, creatinine or calcium, or symptoms suggestive of TLS as defined in [Table 13](#).
- 6 In case of any new deterioration in laboratory values, not fulfilling eligibility criteria and deemed as clinically significant by the Investigator, the Medical Monitor must be contacted to discuss whether AZD4573 dosing can be continued.

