17.1.10.10.3 TLS Prophylaxis, Monitoring, and Management

Please refer to [Appendix F](#) for definitions of the Howard modification of Cairo-Bishop criteria for clinical and laboratory TLS.

All patients will receive TLS prophylaxis during the intra-patient ramp up and be monitored for TLS during the first 24 hours post start of dose. Monitoring for TLS includes checking potassium, calcium, phosphate, uric acid, and creatinine. Fluid balance must be monitored according to institutional standards.

Patients will be required to be monitored for TLS for up to 24 hours post dose until they have received at least one AZD4573 dose at the target dose level (ie, for at least the first 3 AZD4573 once-weekly doses). If a patient has no signs of laboratory TLS at the 6-hour TLS monitoring assessment, the patient may leave the clinic after the collection of other laboratory samples, as per the SoA, at 7 hours after the start of the infusion and managed as an outpatient, at the discretion of the Investigator. These patients must return to the clinic the next morning to complete the 24 hour TLS monitoring period as per the SoA (Cycle 1 Weeks 1-3). Patients with TLS at the 6-hour TLS monitoring assessment must be admitted for in-patient TLS monitoring for a minimum of 24 hours after the start of the infusion and monitored every 4 to 6 hours during this time (or more frequently if clinically indicated).

Sites retain the option to hospitalise patients based on clinical judgement, despite normal TLS laboratory results 6 hours after the start of the infusion. Admitting the patient for subsequent dose administrations will be done at Investigator discretion.

Any hospitalisation due to occurrence of an AE must be reported as an SAE, per definition. However, if hospitalisation is purely for the purposes of extended observation then this does not qualify as an SAE and does not need to be reported.

For all patients, results of safety laboratory testing (haematology and clinical chemistry at a minimum) must be available within 72 hours prior to dosing and must be reviewed by the Investigator prior to each administration of AZD4573.

In particular, the uric acid level must be < ULN prior to the start of each AZD4573 infusion.

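### Table 13 lowers AZD4573 by one level when pre-dose TLS-type laboratory changes have not resolved after a 7-day hold, without requiring recovery; this conflicts with the uric-acid rule and, less firmly, with the retreatment criteria

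*Protocol*

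**What the plan says.** The first TLS row of Table 13 (Section 15.12) covers changes in uric acid, potassium, phosphorus, creatinine or calcium, or symptoms that the investigator judges suggestive of clinically significant TLS. For abnormal changes already present before dosing, the AZD4573 column calls for supportive therapy and then says to "hold drug for up to 7 days. If not resolved, reduce by 1 dose level".

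Section 15.12.1 lists retreatment conditions for all participants, described as "criteria to be met before participant restarts study drug infusions". Item 4 requires uric acid to be back below ULN. Item 5 reads "Recovery of changes in uric acid, potassium, phosphorus, creatinine or calcium, or symptoms suggestive of TLS as defined in" Table 13.

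Section 17.1.10.10.3 states separately that "the uric acid level must be < ULN prior to the start of each AZD4573 infusion". Table 16 footnote d repeats the uric-acid condition for each AZD4573 dose, worded as a should.

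Retreatment is defined twice. The Core definition (Section 6.12.1) is the first dose after an intentional pause. The Module 1 definition (Section 15.12.1) adds that the pause be significant, a word it does not define. Both exclude missed doses.

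**The concern.** The Table 13 cell limits the hold to 7 days and then gives an instruction that takes effect precisely when the abnormality has not cleared. It states neither a recovery condition nor a stop. A site working from the table alone would end the hold and give AZD4573 one level lower. A site working from the TLS section or the retreatment criteria would not infuse.

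At stake is the handling of the first important identified risk listed for AZD4573 in Section 2.3.1. Sections 15.12.1 and 17.1.10.10 both send the reader to Table 13, so the table is where a site is likely to look. Recruitment has stopped (Section 4.1), but Section 6.13 lets participants who still benefit continue treatment under the guidance in this protocol and the investigator's brochure. Under Section 17.1.6, chemistry covering these analytes is drawn before AZD4573 infusions in later cycles too. The row is therefore still in use and is not confined to the ramp-up.

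**Working it through.** No arithmetic applies. The check sets the passages side by side and works through two cases.

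1. **Trigger and action in Table 13.** The trigger is an abnormality before dosing that has not resolved by the end of a hold of at most 7 days. The action is a reduction by one level. Recovery is not mentioned.

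2. **Is recovery implied by the rest of the table?** The neighbouring AZD4573 entries state it. Grade 1 or 2 TLS resumes at the same level once resolved. A first Grade 3 event resumes after resolution to Grade 1. A second Grade 3 event is reduced by one level, expressly after resolution to Grade 1. The table therefore says so where a reduction is meant to follow recovery. The pre-dose entry does not, and its condition is the opposite.

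3. **Case A: uric acid still above ULN after the 7-day hold.**
   - Table 13: AZD4573 one level lower.
   - Section 17.1.10.10.3: no infusion, because the condition is mandatory before every infusion.
   - Table 16 footnote d: same direction, in weaker wording.
   - Section 15.12.1 item 4: no restart.
   - The rule in 17.1.10.10.3 applies whether or not the infusion counts as retreatment, so the conflict in this case does not depend on that definition.

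4. **Case B: potassium, phosphorus, creatinine or calcium still abnormal after the hold, uric acid below ULN.**
   - Table 13: AZD4573 one level lower.
   - Section 17.1.10.10.3 and Table 16 footnote d: silent on these analytes.
   - Section 15.12.1 item 4: met.
   - Section 15.12.1 item 5: calls for recovery, but by reference to Table 13, the text in question. It also applies only if the hold is a pause within the retreatment definition. Section 15.3 equates a delay of more than approximately 7 days with more than one missed dose, so a hold of up to 7 days can be argued to be a single missed weekly dose. Against that, a Table 13 hold is intentional, and the Core definition does not require the pause to be significant.

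5. **Result.** Case A is a direct contradiction. Case B is a conflict on one reasonable reading and an unanswered question on the other.

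**The case against.** The best defence is that the cell never says to resume or infuse, whereas the graded entries beside it do. On that view it sets only the level of the next dose, and whether a dose is given is decided elsewhere: by the uric-acid rule, by the retreatment criteria, by laboratory review before each administration, and by the Medical Monitor discussion that Section 6.12 requires before dosing resumes after a clinically significant, possibly related reaction. Table 13 is also headed as recommended, so a mandatory rule should prevail over it.

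Part of this stands. A careful investigator with raised uric acid would probably not infuse, and for the other four analytes the text can be read without contradiction. But the reader has to supply the missing condition, no precedence between the passages is stated, and the item that might settle the matter points back to the table.

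A reader might also infer several stronger points that the documents do not support:

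- **The acalabrutinib cell of the same row forbids AZD4573 dosing.** It withholds acalabrutinib until resolution and governs that drug only.
- **The DLT rule contradicts the row.** Laboratory TLS "will be considered a DLT if the metabolic abnormalities do not resolve within 5 days despite protocol-recommended management". That is a classification and can coexist with a 7-day hold. Section 6.12 allows dosing to be halted or reduced after a DLT, and the row is broader than laboratory TLS.
- **Section 13.1 forbids reduction in Cycle 1.** It says "After completion of the 5-week DLT-assessment period, dose reduction of AZD4573 with each cycle or within a cycle may be applied", which permits reduction later without expressly prohibiting it earlier. With recruitment stopped, harm inside the DLT window is also largely moot.
- **The first-in-human TLS figure measures how often this occurs.** The 16 of 38 participants (42.1%) had laboratory evidence of TLS on monotherapy. The figure does not count changes present before a dose and still unresolved 7 days later.

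**Conclusion.** The concern holds as an internal contradiction in current text. It is firm for uric acid: one passage leads to a reduced infusion and another bars any infusion until the level is below ULN. It is less firm for potassium, phosphorus, creatinine and calcium, where it depends on treating a Table 13 hold as a pause within the retreatment definition and on reading item 5 as an independent requirement despite its reference to Table 13.

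The conclusion assumes that an instruction to reduce, following a time-limited hold, means that dosing continues at the lower level. The wording supports this, because the neighbouring second Grade 3 entry states recovery first and this one does not.

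The documents do not allow a frequency to be put on the affected branch, and no statistical quantity changes. Correction is warranted because the step is safety-critical, continuing participants are still dosed under this protocol, and the change is small. Nothing here implies which clinical rule is right.

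**What to change.** Reconcile the AZD4573 cell in the first TLS row of Table 13 with Section 15.12.1 items 4 and 5, Section 17.1.10.10.3 and Table 16 footnote d. Together they should give one answer to two questions: whether AZD4573 may be given while any of these parameters is unresolved, and what happens when the 7-day hold ends. Put that answer in item 5 in place of the reference back to Table 13. State whether a Table 13 hold counts as a pause under the retreatment definition, and align the Core and Module 1 definitions on the word significant. The clinical team decides the content of the rule.

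The cost is a wording amendment to these passages and a site memo. No visits, samples or analyses are added. Module 2 has a table of the same title (Table 31 in the list of tables), and the same check is worth making there.

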6.12 Dose Modification

If, in the opinion of the Investigator, a participant experiences a clinically significant and/or unacceptable adverse reaction, including a DLT not attributable to the disease or disease-related processes under investigation, but is considered to be possibly related to AZD4573 by the Investigator, then the dose may be temporarily or permanently halted or reduced.

Supportive therapy will be administered as required. Relevant reporting and discussion with the Medical Monitor will take place before resumption of dosing.

Events meeting the definition of a DLT as defined in the specific study modules must be

reported accordingly. Refer to specific study modules for dose modifications.

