- A delay in dosing of more than approximately 7 consecutive days (\pm 2 days), in other words, more than 1 missed dose, due to a dose-related toxicity occurring during the 5-week DLT-assessment period (toxicity that is clearly and directly related to the primary disease or to another aetiology is excluded from this definition).

Isolated elevations of transaminases:

- Grade 3 elevations ($\geq 5 \times$ ULN) in ALT or AST, without concomitant elevation in total bilirubin $> 2 \times$ ULN, that do not return to Grade 1 within 7 days from start of dosing.
- Grade 4 elevations in ALT ($\geq 20 \times$ ULN) of any duration irrespective of total bilirubin.
- Grade 4 elevations in AST ($\geq 20 \times$ ULN) without concomitant elevation in ALT $\geq 20 \times$ ULN or total bilirubin $\geq 2 \times$ ULN that do not return to Grade 1 within 7 days from start of dosing.

Elevations in transaminases with concomitant elevation of bilirubin (Potential Hy's Law [PHL]):

- Elevations in ALT or AST $\geq 3 \times$ ULN with concomitant elevation in total bilirubin $\geq 2 \times$ ULN where bilirubin does not return to meet initial eligibility criteria within 72 hours of onset or 96 hours of start of dosing (-2/+12 hours) whichever is the sooner, and/or ALT or AST do not return to meet initial eligibility criteria within 7 days post start of dose.
- Elevations in ALT or AST $\geq 3 \times$ ULN with concomitant elevation in total bilirubin $\geq 2 \times$ ULN and INR $> 1.5 \times$ ULN (or $> 1.5 \times$ baseline, if elevated at baseline) of any duration.
- Elevations in ALT or AST $\geq 3 \times$ ULN with concomitant elevation in total bilirubin $\geq 2 \times$ ULN of any duration if associated with symptoms or signs of liver impairment (eg, appearance of fatigue, nausea, vomiting, right upper quadrant pain or tenderness, fever, rash, and/or eosinophilia $> 5\%$).

Any of the following haematological toxicities:

- CTCAE Grade 4 neutrophil count decrease lasting > 7 days, despite growth factor support.
- Grade ≥ 3 febrile neutropenia (absolute neutrophil count [ANC] $< 1.0 \times 10^9/L$, fever $> 100.9^{\circ}\text{F}$ [or $> 38.3^{\circ}\text{C}$]) of any duration despite supportive care.
- CTCAE Grade 4 thrombocytopenia lasting more than 7 days or Grade ≥ 3 thrombocytopenia, of any duration, associated with \geq Grade 2 bleeding.

- CTCAE Grade 4 anaemia despite transfusion.

Any Tumour Lysis Syndrome meeting the following criteria:

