Event ^a	Action	
	AZD4573	Acalabrutinib
Isolated^b elevations in ALT, AST, or bilirubin		
Grade 1 Isolated ALT/AST \leq 3 \times ULN or Isolated Bilirubin \leq 1.5 \times ULN	Maintain current dose level. Monitor ALT, AST, ALP, and bilirubin at least 1x per week.	Maintain current dose level and schedule. Monitor ALT, AST, ALP, and bilirubin at least 1x per week.

Event ^a	Action	
	AZD4573	Acalabrutinib
Grade 2 Isolated ALT/AST > 3 to $\leq 5 \times$ ULN or Isolated Bilirubin > 1.5- $\leq 3 \times$ ULN	After 7 days if hepatic enzymes resolve to Grade ≤ 1 , rechallenge at same dose level.	Withhold or continue acalabrutinib (at Investigator discretion, after discussion with the Medical Monitor). To prevent disease progression, monitor disease parameters closely. Monitor ALT, AST, ALP, and bilirubin at least 1x per week. After 7 days if hepatic enzymes appear to be improving and acalabrutinib was withheld, restart acalabrutinib at current dose level.
Grade 3 Isolated ALT/AST > 5-20 \times ULN	If recovered to Grade ≤ 1 within 7 days, allow rechallenge at same dose level. If not recovered to baseline level within 7 days, discontinue AZD4573.	Withhold or continue acalabrutinib (at Investigator discretion, after discussion with the Medical Monitor). To prevent disease progression, monitor disease parameters closely.
Grade 3 Isolated Bilirubin > 3-10 \times ULN	If recovered to baseline level within 96 hours (-2/+12 hours) of the start of the infusion allow rechallenge at same dose level. If not, discontinue AZD4573	Monitor ALT, AST, ALP, and bilirubin at least 1x per week. After 7 days if hepatic enzymes appear to be improving and acalabrutinib was withheld, restart acalabrutinib with 1 level dose reduction or discontinue.
Grade 4^c Isolated ALT > 20 \times ULN or Isolated Bilirubin > 10 \times ULN	Discontinue AZD4573.	Discontinue acalabrutinib.
Grade 4 Isolated elevation ($\geq 20 \times$ ULN) in AST without concomitant elevation in ALT $\geq 20 \times$ ULN or concomitant elevation in TBL $\geq 2 \times$ ULN that fails to return to baseline level within 7 days from start of dosing	Discontinue AZD4573.	Discontinue acalabrutinib.

Event ^a	Action	
	AZD4573	Acalabrutinib

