Grade 4^c Isolated AST elevation $\geq 20 \times$ ULN without concomitant elevation in ALT $\geq 20 \times$ ULN or TBL $\geq 2 \times$ ULN	1st occurrence If recovered to Grade ≤ 1 or baseline level within 7 days of the start of the infusion allow rechallenge at same dose level 2nd occurrence If recovered to Grade ≤ 1 or baseline level within 7 days of the start of the infusion allow rechallenge with 1 dose level reduction 3rd occurrence Discontinue AZD4573	Withhold or continue acalabrutinib (at Investigator discretion, after discussion with the Medical Monitor). To prevent disease progression, monitor disease parameters closely. Monitor ALT, AST, ALP, and bilirubin at least 1x per week. After 7 days if hepatic enzymes appear to be improving and acalabrutinib was withheld, restart acalabrutinib at current dose level at the 1st occurrence and with 1 level dose reduction at the 2nd occurrence . Discontinue acalabrutinib at the 3rd occurrence .
Concurrent elevations in ALT, AST, or bilirubin (Please also refer to Appendix E for actions to be taken in the event of PHL)		
ALT or AST $\geq 3 \times$ ULN with TBL $\geq 2 \times$ ULN (Potential Hy's Law) AND INR $\geq 1.5 \times$ ULN (or $\geq 1.5 \times$ baseline if elevated at baseline) of any duration	Discontinue AZD4573.	Discontinue acalabrutinib.
ALT or AST $\geq 3 \times$ ULN with the appearance of fatigue, nausea, vomiting, right upper quadrant pain or tenderness, fever, rash, and/or eosinophilia $> 5\%$	Discontinue AZD4573.	Discontinue acalabrutinib.
ALT or AST $\geq 3 \times$ ULN and TBL $\geq 2 \times$ ULN where TBL does not return to baseline level within 96 hours (-2/+12 hours) from start of dose and/or AST or ALT do not return to baseline level within 7 days from start of dose	Discontinue AZD4573.	Discontinue acalabrutinib.

Event ^a	Action	
	AZD4573	Acalabrutinib
Grade 3 elevation ($\geq 5 \times$ ULN) in ALT or AST with TBL elevation above baseline level or ULN, but $< 2 \times$ ULN that do not return to baseline level within 7 days	Discontinue AZD4573.	Discontinue acalabrutinib.

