ALT and AST $\geq 3 \times$ ULN with concomitant TBL $\geq 2 \times$ ULN, NO increase in INR $\geq 1.5 \times$ ULN (or $1.5 \times$ baseline), and NO fatigue, nausea, vomiting, right upper quadrant pain or tenderness, fever, rash, and/or eosinophilia $> 5\%$	If recovered to Grade ≤ 1 or baseline level within 96 (-2/+12) hours, rechallenge at same dose level ^c	Withhold acalabrutinib until recovered. Once recovered, restart acalabrutinib at same dose.

^a Adverse reactions are graded using National Cancer Institute CTCAE version 5.0. All grades refer to CTCAE grading except for TLS, which uses the Howard modification of Cairo-Bishop criteria (Howard et al 2011).

^b Elevations in ALT or AST are considered isolated if bilirubin remains below Grade 1, and elevations in bilirubin are considered isolated if ALT and AST remain below Grade 1.

^c Participants who are considered for rechallenge in the event of Grade 4 transaminase increases or PHL must discuss possible risk of hepatotoxicity with the treating physician, who will document this discussion and participant agreement for continued treatment in the medical records.

Note: Adequate supportive therapy as per institutional guidelines should be given for all toxicities.

Abbreviations: ALP = alkaline phosphatase; ALT = alanine aminotransferase; AST = aspartate aminotransferase; CTCAE = Common Terminology Criteria for Adverse Events; INR = international normalised ratio; PHL = Potential Hy's Law; TBL = total bilirubin; ULN = upper limit of normal.

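### Table 14 uses two recovery benchmarks for isolated transaminase elevations, so a day-7 value above baseline but no higher than 3 x ULN is told both to resume and to stop

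*Protocol*

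**What the plan says.** All of this is in Table 14, Section 15.12 of the protocol, unless noted.

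- **Isolated Grade 3 ALT/AST, AZD4573.** Rechallenge is tied to Grade 1 or lower; the stopping order in the next sentence is tied to baseline: "within 7 days, allow rechallenge at same dose level. If not recovered to baseline level within 7 days, discontinue AZD4573".
- **Isolated Grade 4 AST, first row.** Both drugs are discontinued for an elevation "that fails to return to baseline level within 7 days from start of dosing".
- **Isolated Grade 4 AST, second row.** The AST, ALT and bilirubin definition is the same, with no recovery condition. For AZD4573 at the first occurrence, the test is recovery to Grade 1 or lower "or baseline level within 7 days of the start of the infusion allow rechallenge at same dose level"; at the second occurrence the same test allows a dose one level lower. Acalabrutinib may be withheld or continued after discussion with the Medical Monitor. For a withheld dose: "After 7 days if hepatic enzymes appear to be improving and acalabrutinib was withheld, restart acalabrutinib at current dose level at the" first occurrence, and one level lower at the second. Both drugs stop at the third.
- **Footnote b.** "Elevations in ALT or AST are considered isolated if bilirubin remains below Grade 1".
- **Section 15.3.** The DLT criteria for isolated Grade 3 ALT/AST and isolated Grade 4 AST count only elevations "that do not return to Grade 1 within 7 days from start of dosing".
- **Sections 15.12.1 and 17.1.10.9.** The first makes recovery from hepatic events, within Table 14's time frames, a condition for restarting infusions and, where applicable, capsules. The second requires permanent discontinuation of study treatment if transaminases have not resolved within 7 days. Neither says whether recovery means Grade 1 or baseline.

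**The concern.** Transaminase increase is listed as an important identified risk of AZD4573 (Section 2.3.1), and these cells are the stopping rule for it. Dosing is weekly, so day 7 is when the next infusion is decided. If one laboratory value satisfies both the resume branch and the stop branch, two sites can treat the same participant differently, each with support in the table. An error in one direction re-exposes someone whom the stopping rule would remove. An error in the other permanently ends treatment for someone who, under the Module 1 inclusion criteria, has no standard therapy available.

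The event in the Grade 4 rows has been seen. Section 13.3 reports isolated Grade 4 AST elevations in 2 of 6 DLT-evaluable participants at 12 mg in the first-in-human study, and 12 mg is dose level 2 here. Those elevations lasted less than 4 days, and the protocol does not say where the values stood relative to baseline on day 7.

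**Working it through.** No sample size or error rate is involved. The check writes each rule as a condition on the day-7 value and looks for overlap.

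**Inputs, in multiples of ULN**

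- Upper limit of Grade 1 for ALT/AST: 3 (Table 14).
- Entry limit for ALT/AST: below 3.0 (Section 5.1, Table 2).
- Assumption: normal means at most 1.0.
- The text at hand does not define baseline level, so two readings are taken: the participant's own value B, or the grade at baseline.

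**Overlap, with V the day-7 value**

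- Resume branch: V ≤ 3.
- Stop branch, value reading: V > B.
- Both hold when B < V ≤ 3, so the width is 3.0 − B.

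| Assumed B | Width of overlap |
|---|---|
| 0.5 | 3.0 − 0.5 = 2.5 |
| 0.8 | 3.0 − 0.8 = 2.2 |
| 1.0 | 3.0 − 1.0 = 2.0 |
| 2.0 | 3.0 − 2.0 = 1.0 |

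With the screening value as baseline, B is below 3.0, so on the value reading the overlap is never empty. On the grade reading it is 3.0 − 1.0 = 2.0 wide for a normal baseline, and empty for a participant already at Grade 1 on entry.

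**Isolated Grade 3 ALT.** Baseline 0.8, peak 6, day 7 at 2.0, bilirubin normal. Since 2.0 ≤ 3, rechallenge is allowed. Since 2.0 > 0.8, and Grade 1 is worse than normal, discontinuation is ordered on both readings. With baseline 1.5 instead, the clash arises on the value reading only.

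**Isolated Grade 4 AST, first occurrence.** Baseline 0.8, peak 25, ALT below 20, bilirubin normal, day 7 at 2.0.

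| Drug | First row | Second row |
|---|---|---|
| AZD4573 | discontinue (2.0 > 0.8) | rechallenge allowed (2.0 ≤ 3) |
| Acalabrutinib, if withheld | discontinue | restart (25 down to 2.0 is improving) |

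The same value is not a DLT, because 2.0 is within Grade 1.

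**Where the Grade 4 rows do not clash.** If AST is at baseline by day 7, only the second row applies. At the third occurrence both rows stop both drugs. Above 3, neither row lets AZD4573 resume.

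**Does other text choose the benchmark?**

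- Sections 15.12.1 and 17.1.10.9 leave recovery and resolution undefined. They settle values above 3, which meet neither benchmark, but not values between baseline and 3.
- Section 6.12 says "discussion with the Medical Monitor will take place before resumption of dosing", and Section 17.1.6 requires contact with the Medical Monitor if an event is unresolved at 96 hours. Both prescribe a conversation, not a threshold.
- Footnote c makes the treating physician responsible for a risk discussion, "who will document this discussion and participant agreement for continued treatment in the medical records". It covers Grade 4 transaminases and potential Hy's Law, not the Grade 3 cell, and sets no benchmark.

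**The case against.** The Grade 3 cell has a safe default. Rechallenge is a permission and discontinuation an order, so a site that always stops complies with both. That is correct for AZD4573, but it leaves the Grade 1 permission with no effect above baseline. It does not carry over to acalabrutinib in the Grade 4 rows, where restart and discontinue are both directions.

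The two Grade 4 AST rows can be reconciled by reading the first as the specific case of non-recovery and the second as everything else. This is a fair reading of intent. However, the second row's event definition contains no recovery condition, its Grade 1 wording would then be idle, and an improving enzyme is by nature one that has not yet recovered.

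The table is headed as recommendations, and Medical Monitor discussion is built into the acalabrutinib cell itself. Yet Section 17.1.10 says Grade 3 and 4 toxicities require modification as the tables describe, and Section 15.12.1 makes Table 14's time frames a condition of retreatment.

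Recruitment has stopped (Section 4.1), which limits exposure. Section 6.13 still has participants who continue after data cut-off dosed under this protocol and the Investigator's Brochure. Section 15.7 also refers them to the current brochure, which is not at hand.

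A reader might infer two stronger points that the documents do not support. The first is that withheld acalabrutinib would be restarted at any improving AST, even 8 x ULN on day 7. Section 17.1.10.9 requires study treatment to stop if transaminases have not resolved within 7 days, and Section 13.1 explains study treatment as both drugs. Section 15.12.1 also requires recovery before capsules restart. Such a value ends in discontinuation. The second is that the potential Hy's Law rows contain an equally open conflict. Those rows send the reader to Appendix E, which is not in the text at hand, and the mandatory wording in Sections 15.2 and 17.1.10.9 largely settles the action.

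**Conclusion.** The point holds in a bounded form. Table 14 gives incompatible instructions for AZD4573 after an isolated Grade 3 ALT/AST elevation. It does so for both drugs after a first or second isolated Grade 4 AST elevation. In each case the day-7 value must lie above baseline and at or below 3 x ULN. On the value reading that band is 1.0 to 2.5 x ULN wide for the assumed baselines. On the grade reading it is 2.0 x ULN wide for a normal baseline and absent for a Grade 1 baseline. A participant with a normal baseline and a day-7 value of 2.0 x ULN is caught on either reading.

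Above 3 x ULN the outcome is discontinuation, and the second Grade 4 row's improving trigger is simply out of line with the mandatory sections. The protocol does not say how many participants fell in the band or remain on treatment.

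This is a minor safety-wording correction. It should not be read as casting doubt on the DLT definition, the MTD or the response analyses. Section 15.3 uses Grade 1 for these isolated elevations and does not depend on Table 14.

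**What to change.** - Use one benchmark in both the rechallenge and the discontinue branch for isolated Grade 3 ALT/AST and isolated Grade 4 AST. Grade 1 or lower, or baseline, would fit the Section 15.3 benchmark. The isolated Grade 3 bilirubin row already works with a single benchmark. The clinical choice belongs to the sponsor's hepatic experts.
- State whether baseline level means the participant's value or grade.
- Merge the two isolated Grade 4 AST rows into one, with a single acalabrutinib action per occurrence, and replace the improving trigger with the same benchmark.
- Use the same term for recovery in Sections 15.12.1 and 17.1.10.9.

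The cost is a wording correction by protocol clarification or site letter. No data, endpoint or DLT count changes.
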